This study is designed to evaluate a transdiagnostic CBT specifically constructed to treat Veterans with depressive/anxiety disorders. The protocol includes both a primary transdiagnostic exposure component as well as supplementary disorder-specific modules to address ancillary symptoms. This transdiagnostic CBT has been investigated through focus groups with Veterans and two pilot demonstrations. This study will compare transdiagnostic CBT to an existing evidence-based version of CBT, behavioral activation therapy (BAT; psychotherapy control condition). A randomized controlled trial (RCT) of 96 DVA patients with depressive/anxiety disorders will be conducted to examine its efficacy, feasibility, and accessibility. Diagnostic interviews and self-

report symptom questionnaires will be completed at pre-treatment, immediate post-treatment, and 6-month followup assessment time points.

Research Primary Aim 1: To examine efficacy of transdiagnostic CBT on reducing transdiagnostic and disorderspecific mental health symptoms and improving quality of life at immediate post-treatment and 6-month follow-up. Hypothesis 1: The transdiagnostic CBT will result in significantly greater reductions in symptomatology (for principal and comorbid diagnoses) and improvements in quality of life compared to the BAT control condition at immediate post-treatment and 6-month follow-up. Although limited specific symptoms may ultimately be comparable across treatments (e.g., depression), the transdiagnostic CBT will demonstrate significantly greater reductions in the majority of symptoms (e.g., anxiety, panic, fear, stress).

Research Primary Aim 2: To examine feasibility and acceptability of transdiagnostic CBT

Hypothesis 2: The transdiagnostic CBT will be well tolerated by DVA patients as demonstrated by improved attendance and dropout rates, patient satisfaction questionnaires, and positive feedback in post-treatment patient interviews as compared to the BAT control condition. This hypothesis is based on the predicted greater symptom improvement (hypothesis 1) as well as the flexibility and individual tailoring of the treatment approach incorporated within transdiagnostic CBT.

B. BACKGROUND AND SIGNIFICANCE

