Eligible VAMC patients will be randomized into one of two treatment conditions: transdiagnostic CBT or an existing evidence-based version of CBT (BAT). Both treatment conditions will include 12-16 weekly 45-60-minute individual psychotherapy sessions. The total number of sessions will vary slightly depending on participant needs and progress during therapy, as is common in most CBT approaches to psychotherapy (and will serve as a covariate in the outcome analyses). The general format of sessions will involve: 1) brief check-in; 2) review of materials from previous sessions; 3) review of homework assignments; 4) overview of new materials and insession exercises; and 5) assignment of homework for next session. Attendance and homework completion will be recorded. A full battery of self-report questionnaires and a diagnostic interview will be completed pretreatment, post-treatment, and at the 6-month follow-up to track participants' progression through treatment and maintenance. Post-treatment participant interviews will be completed at immediate post-treatment and 6-month follow-up to collect feedback on participants' perspectives on the treatments.

Table of Procedures for Each Visit – Summarized Across Treatment Conditions

Week	Content	Assessment Summary
1	Pre-Treatment Assessment	Clinical interview & self-report battery (7 measures)
2	Session 1: Psychoeducation	Brief self-report battery (3 measures)
3 4 5	Session 2: Treatment planning Session 3: Introduction to behavior therapy Session 4: Behavior therapy	Brief self-report battery (3 measures)
6	Session 5: Behavior therapy	Brief self-report battery (3 measures)
7 8	Session 6: Behavior therapy Session 7: Behavior therapy	Brief self-report battery (3 measures)
9 10 11	Session 8: Behavior therapy Session 9: Behavior therapy Session 10: Behavior therapy	Brief self-report battery (3 measures)
12 13	Session 11: Behavior therapy Session 12: Behavior therapy	Brief self-report battery (3 measures)
14	Session 13: Behavior therapy (as needed)	Brief self-report battery (3 measures)
15 16 17	Session 14: Behavior therapy (as needed) Session 15: Behavior therapy (as needed) Session 16: Relapse prevention (as needed)	Brief self-report battery (3 measures)
~18	Post-Treatment Assessment	Clinical interview, immediate treatment interview, & self-report battery (7 measures), treatment satisfaction

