~33	6-Month Follow-Up Assessment	Clinical interview, immediate treatment interview, & self-report battery (7 measures), treatment satisfaction

Note. Behavior therapy involves the introduction, teaching, in-session and between-session practice, and mastery of behavioral therapeutic techniques designed to improve symptoms of depression and anxiety, including behavioral activation (BAT group) as well as situational, physical, thought, and emotional exposures (transdiagnostic CBT group). Final treatment session will take place between sessions 12-16, as determined by provider and participants' collective decision. Final treatment session will involve relapse prevention content. Post-treatment assessment will be completed 1 week immediately after final treatment session. 6-month follow-up assessment will be completed 6-months after final treatment session.

Randomization Procedures

Participants will be randomly assigned (1:1) to one of the two study arms (*n* = 48 per arm) using a permuted block randomization procedure. Randomization will be stratified by principal diagnostic group and block size will be varied to minimize the likelihood of unmasking. After determining eligibility and completing consent and baseline assessment materials, enrolled participants will be assigned to treatment groups by the Project Research Assistant using a computer generated randomization scheme. Once a participant is randomized and attends the first session, they will be included in the intent-to-treat analysis. Randomization will occur at the participant level. As such, we will take the following steps to minimize contamination between the two arms of the study: 1) only one member of a household will be eligible for enrollment; and 2) other VAMC providers will be informed of their patients' participation in the study, but will be blinded to the treatment condition of their patients.

Transdiagnostic CBT Treatment Condition

As noted above in the Preliminary Studies section, a transdiagnostic CBT protocol was developed and revised through two demonstration studies and one focus group. The resulting protocol involves several primary components, including psychoeducation on the symptoms of depression and anxiety (session 1), assessment of motivation and setup of treatment plans (session 2), exposure therapy (sessions 3-15), and relapse prevention (final session). In addition to these primary components, optional modules are included to supplement exposure

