The full intent to treat (ITT) analysis set will comprise all randomized participants. Missing data in the full analysis set will occur if participants drop out prior to the end of the study. Participants will not be discontinued from the study because of non-adherence and all will remain in the study unless consent is withdrawn or if there are concerns regarding participant safety. Missing data for the ITT analysis set will be imputed using multiple imputation methods. The results of analyses using study completers and protocol adherers (completer and perprotocol analyses) will be compared with results using the ITT analysis set to test sensitivity of study conclusions to study drop-outs and protocol non-adherence. In addition, the information on dropout proportion will be used as one of the outcome measures of intervention feasibility.

Efficacy (Symptomatology & Quality of Life) Measures Analyses (Primary Aim 1)

The continuous measures of intervention efficacy and quality of life are APPQ, DASS, IIRS, MASA, PCL, STICSA, and V/SF-36. The primary outcome time point is at the end of the active intervention phase (immediate post-treatment) and the secondary time point is at the end of the naturalistic 6-month follow-up period. The difference in mean change from baseline to end-of-active intervention (effect sizes) for transdiagnostic CBT versus BAT control condition will be estimated via 95% CI. For the secondary time-point analyses, transdiagnostic CBT versus BAT control differences in change from immediate end-of-intervention to the 6-month follow-up will also be estimated using 95% CI. By assessing the magnitude of the between-intervention-group differences, as described by the CI, clinicians can judge whether the novel intervention provides sufficient improvement in these outcomes to suggest a clinically significant result that warrants further investigation.

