In preliminary hypothesis testing, efficacy outcome variables will be compared using the generalized linear mixed models (GLMM) approach. This approach provides a general framework that accommodates a wide range of data types (continuous, ordinal, dichotomous, categorical, count) and distributional assumptions (e.g. Gaussian, Binomial, Poisson) and accommodates repeated measures, covariate structure among repeated observations, and missing data. In the first set of primary hypothesis testing analyses, immediate post-treatment scores for each outcome of interest will be used (separately) as the dependent variable in the model, intervention (transdiagnostic CBT versus BAT control) will be included as the primary independent variable, and pre-treatment scores for the outcome of interest will be added as covariates. When approximate normality is assumed, GLMM reduces to a general linear models (GLM) approach which, in the simplest case (intervention as the primary independent variable with baseline level of outcome variable as covariate), is equivalent to a comparison of change from baseline scores for transdiagnostic CBT versus BAT control using an independent sample t-test. Additional covariates (e.g. age, number of psychiatric comorbidities, race, sex, combat theatre, and number of treatment sessions) will be added to the model to adjust for putative confounding variables. If intervention differences in other baseline variables are found in initial descriptive analyses, these variables will be also be added to the multivariable model. In secondary analyses, the modeling procedure will be repeated for the period between immediate post-treatment and 6-month follow-up. Given that we are seeking preliminary evidence of treatment

efficacy (to justify the next step in this line of research), there will be no adjustment for multiple outcomes or time points to avoid an overly conservative approach at this preliminary stage.

Feasibility and Acceptability Analyses (Primary Aim 2)

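### Number of treatment sessions, settled after randomisation and partly by progress, is a planned covariate in the adjusted efficacy models, so their arm coefficient can be biased in either direction

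*Combined protocol and SAP*

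**What the plan says.** Section D, Efficacy Measures Analyses (Primary Aim 1), first describes a model with arm and pre-treatment score: "In the first set of primary hypothesis testing analyses, immediate post-treatment scores for each outcome of interest will be used (separately" as the dependent variable. It then widens the model to deal with suspected confounding: "Additional covariates (e.g. age, number of psychiatric comorbidities, race, sex, combat theatre, and number of treatment sessions) will be added to the model". For follow-up it says that "the modeling procedure will be repeated for the period between immediate post-treatment and 6-month follow-up".

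Section D, Procedures, makes the same commitment without the e.g. and without restricting it to particular analyses. The count depends on needs and "progress during therapy, as is common in most CBT approaches to psychotherapy (and will serve as a covariate in the outcome analyses").

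The same section explains how the count arises: "The total number of sessions will vary slightly depending on participant needs and progress during therapy". The note to the table of procedures adds: "Final treatment session will take place between sessions 12-16, as determined by provider" and participant together. The BAT Control Condition section gives the control arm the same 12-16 session course.

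Section A, Hypothesis 2, predicts better attendance and dropout under transdiagnostic CBT, and gives as one reason: "This hypothesis is based on the predicted greater symptom improvement (hypothesis 1").

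**The concern.** A confounder of a randomised comparison has to precede assignment. The other covariates named in the list are characteristics the participant brings to the trial; session count is not. It is fixed after randomisation and responds to how the participant is doing, which is close to the outcome itself.

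Two distortions are possible. If good progress changes the number of sessions and arm improves progress, conditioning on sessions removes part of the real effect. If arm also shifts sessions for other reasons, the adjusted comparison sets participants with different prognoses against each other. It can then show an effect where there is none, or inflate or shrink a real one.

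An arm link is plausible on the trial's own terms. Hypothesis 2 expects attendance and dropout to differ by arm, partly through symptom improvement. Optional modules are described for the transdiagnostic arm. The safety monitoring plan (Section E.5) offers other treatment when there is no improvement by session 8, which is a further route from progress to session count.

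At stake is a reader taking the adjusted coefficient as the effect of being assigned to transdiagnostic CBT.

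**Working it through.** The plan has no figure of its own to reproduce here. It gives no session distribution, and no significance level, power or target effect behind the 96.

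**Inputs from the documents.** 48 per arm (Randomization Procedures); at least 72 completers (Recruitment Strategy), so 72/2 = 36 per arm; 12-16 sessions.

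**Assumptions.** Outcome SD 1, with negative values favouring transdiagnostic CBT. Baseline-outcome correlation 0.5, so residual SD = √(1 - 0.25) = 0.866. True effect δ = 0 or -0.50 SD. Two-sided 5% test. Session propensity has correlation r = ±0.2 or ±0.4 with residual outcome, and a direct arm shift s = ±0.3 or ±0.5 SD where there is one. It is cut into whole sessions spread evenly over 12-16 (SD about 1.4). Data are complete. The 36-per-arm figures treat completers as a random sample.

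**Without the session term.** SE = 0.866 × √(2/48) = 0.177 at 48 per arm and 0.866 × √(2/36) = 0.204 at 36. In simulation the bias is 0, type I error about 5%, and power at -0.50 about 79% and 67%.

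**With the session term, before rounding to whole sessions.** The coefficient on session propensity is 0.866r, and the arm estimate loses that times the arm difference in propensity.

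- No arm link: estimate = δ.
- Sessions follow progress, including progress caused by arm: the arm difference is rδ/0.866, so estimate = δ(1 - r²). At r = 0.2, -0.50 × 0.96 = -0.48; at r = 0.4, -0.50 × 0.84 = -0.42.
- Direct arm shift, with sessions related to residual outcome only: estimate = δ - 0.866rs. The bias runs from 0.866 × 0.2 × 0.3 = 0.052 to 0.866 × 0.4 × 0.5 = 0.173, either way.
- Both routes: estimate = δ(1 - r²) - 0.866rs. Extremes are -0.42 + 0.173 = -0.247 and -0.42 - 0.173 = -0.593.

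**After rounding to whole sessions (20,000 simulated trials per setting).**

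| Setting | Type I error, 48 / 36 per arm | Estimate when true effect is -0.50 | Power, 48 per arm | Power, 36 per arm |
|---|---|---|---|---|
| Progress only | 5% (no bias under the null) | -0.48 to -0.43 | 77%-72% | 64%-59% |
| Direct shift (0.40-0.65 session) | 5%-15% / 6%-12% | -0.35 to -0.65 | 52%-97% | 41%-90% |
| Both (net difference 0.09-0.92 session) | as for direct shift | -0.28 to -0.58 | 35%-93% | 27%-85% |

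With no arm link, bias is 0 and type I error 5%.

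**Check on the session spread.** Pilot completers averaged 11.5 and 11.8 sessions (Section C), so counts may cluster near 12. With 60/20/10/6/4% at 12 to 16 (SD about 1.1), 48 per arm and 10,000 trials per setting, the direct-shift case gives bias 0.03-0.13 SD, type I error 5%-12%, and -0.37 to -0.63. The combined case gives -0.30 to -0.57 with power 40%-91%. The pattern is the same and somewhat smaller.

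**Check on link strength.** Under stronger assumed links (slow responders stay longer, correlation of sessions with post score about 0.4, arm adding about 0.9 session), a true effect of 0 is estimated at -0.34 and type I error is 52%. Reversing the shift gives +0.34. With progress alone shortening treatment by about 0.6 session, -0.50 becomes -0.27. With no arm effect on sessions, the estimate stays at -0.50. The size follows the assumptions; that bias can go either way does not depend on one choice of them.

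**The case against.** The strongest reply is that sound analyses already carry much of the efficacy reading. Clinicians are to judge the result from the confidence interval for "The difference in mean change from baseline to end-of-active intervention (effect sizes"), which has no session term. The sentence introducing the primary tests names only arm and pre-treatment score. That stands, and it limits the harm to the session-adjusted tests. But the plan never says that the baseline-only model is primary, and Procedures applies the covariate to the outcome analyses generally.

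Second, the mechanism the plan states is progress, and progress alone gives a modest, conservative effect: at most 0.07 SD, against a 95% half-width of about 1.96 × 0.177 = 0.35 SD. That stands for those link strengths. The larger distortions need a direct arm shift, which the documents make possible but do not show. The plan expects only slight variation and gives both arms the same range, although a common permitted range does not equalise the realised counts. Hypothesis 2 also concerns attendance and dropout rather than agreed course length.

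Third, the simulations omit early leavers, counts below 12 and multiple imputation. That also stands, and the figures should be read accordingly.

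Fourth, the follow-up analysis starts from the post-treatment score, itself post-randomisation. Removing sessions would not by itself make that analysis an estimate of the effect of assignment.

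Finally, the trial is preliminary. But its results are meant to justify the next study, so a misread coefficient still matters.

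**Conclusion.** The concern holds. The plan commits in two places to adjusting efficacy for a variable settled after randomisation and partly by response. The justification given, confounding, cannot apply to it. The session-adjusted arm coefficient need not be the effect of assignment and can err in either direction.

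The textual point is firm; the size is conditional. It ranges from zero with no arm link, through a small loss of effect if only progress matters, to type I error of about 15% and estimates between about -0.28 and -0.65 for a true -0.50 at the link strengths in the table. Other link strengths give other sizes. The 6-month model was not simulated, though as written the session term carries over to it. Because unaffected estimates are also planned, this is a defect to correct before analysis rather than one that undermines the trial.

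**What to change.** - Delete number of treatment sessions from the covariate list in Efficacy Measures Analyses, and delete the parenthetical commitment to it in Procedures.
- Restrict additional covariates in the efficacy models to variables measured before randomisation, including when the procedure is repeated to 6 months. By the same reasoning this keeps medication change during treatment, a possible covariate under Treatment Training and Fidelity, out of those models.
- State that the model with arm and pre-treatment score is the primary test at immediate post-treatment, with further baseline covariates as supporting analyses.
- Report session count and medication change by arm.
- Label any session-adjusted, dose-response or mediation analysis exploratory, and say that it does not estimate the effect of assignment.

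The cost is analysis wording only: no new data, participants or staff, and no change to the treatment delivered.

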Our software (logical) security policy has three main components: 1) VAMC standard antiviral protection; 2) password policies; and 3) additional level of firewall protection. The National DVA maintains firewall protection. The backup schedule at the RHJ VAMC consists of fully-verified daily backups. The backup tapes, which are in current rotation, are stored locally.

All data will be entered into an SPSS database. The SPSS database will be created by the Principal Investigator and research assistant will be responsible for all data entry. Data quality and consistency checks (e.g., data range checks) will be integrated as part of the data entry procedure. Data quality will be monitored and assured in several ways: 1) as reported; and 2) as entered into the study database. For the former, all hardcopy data forms will be visually inspected by project staff prior to data entry. Furthermore, a manual comparison of randomly selected data hardcopy forms with data output generated from the SPSS database will be performed, and consistency checks will be generated as part of routine data cleaning procedures. All hardcopies of the data files will be stored in a locked file cabinet behind a locked door in the PI's office at the RHJ VAMC (B530). Hardcopies of the data will be destroyed/shredded at five years after the completion of the study.

Analysis Plan – Treatment Outcome Symptomatology and Feasibility

Preliminary Descriptive Analyses

Univariate descriptive statistics and frequency distributions will be calculated as appropriate for all relevant variables to identify potential departures from distributional assumptions of proposed analyses. If necessary, appropriate data transformations will be applied, or alternative analysis procedures (e.g., nonparametric) will be used. Baseline values for demographic and symptom variables will be described via frequency distributions for categorical variables, measures of central tendency (mean, median), and variability for the total sample and within race groups. The baseline variables will be compared between intervention groups using t-tests (or Wilcoxon rank sum tests) for continuous outcomes and chi-square (or Fisher's Exact Test) for categorical variables.

Missing Data

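### Baseline significance tests between randomised arms feed extra covariates into the efficacy model, so part of that model is chosen by chance imbalance and is not fixed before arm-level data are seen

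*Combined protocol and SAP*

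**What the plan says.** Three statements in Section D of the combined protocol and SAP together define the efficacy model.

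- **Preliminary Descriptive Analyses.** Demographic and symptom variables are summarised and then tested between arms: "The baseline variables will be compared between intervention groups using t-tests (or Wilcoxon rank sum tests) for continuous outcomes", with chi-square or Fisher tests for categorical variables. No significance level is given.
- **Efficacy Measures Analyses (Primary Aim 1), fixed part.** "In the first set of primary hypothesis testing analyses, immediate post-treatment scores for each outcome of interest will be used (separately) as the dependent variable". Besides treatment arm, "pre-treatment scores for the outcome of interest will be added as covariates". Then: "Additional covariates (e.g. age, number of psychiatric comorbidities, race, sex, combat theatre, and number of treatment sessions) will be added to the model". These terms do not depend on balance, but the list is given as examples and is not closed.
- **Same section, data-driven part.** "If intervention differences in other baseline variables are found in initial descriptive analyses, these variables will be also be added to the multivariable model".

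The modelling is done separately for seven instruments and repeated for the follow-up period. The Aim 2 and exploratory analyses reuse the same framework. Nothing elsewhere in the document overrides the rule. Randomisation is stratified by principal diagnosis (Randomization Procedures), but that factor is not among the covariates named for the main model.

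**The concern.** Allocation is random, so a baseline test examines a null hypothesis already known to be true. A significant result is a chance event and carries no information on whether the variable predicts outcome. Passing the result into the model has three effects:

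- some covariates enter because they happen to be imbalanced and not because they are prognostic;
- a prognostic variable outside the named list is left out whenever it happens to be balanced;
- the final model cannot be written down until data have been examined by arm.

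With 96 randomised and a target of at least 72 completers, precision is scarce and is better obtained from covariates chosen for prognosis. Since the plan does not define a difference, the choice of model is also open to challenge once results are known.

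**Working it through.** The documents give no alpha, power or error rate for this rule, so there is no figure of the plan's own to reproduce.

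**Step 1: count the candidates.** The Demographic Intake Questionnaire (Appendix) has age plus ten numbered questions, so 11 items. Age, race, sex and combat theatre are already named covariates: 11 − 4 = 7. There are seven outcome instruments, and for any one outcome the other six are candidates. Total: 7 + 6 = 13. Scoring subscales separately would raise this.

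**Step 2: chance of a spurious difference.** Assume a 0.05 threshold. For independent candidates the chance of at least one is 1 − 0.95^13 = 0.487, and the expected number is 13 × 0.05 = 0.65. With candidates correlated 0.5, simulation gives about 33%.

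**Step 3: simulate the rule.** Three linear models were compared:

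- A: arm and pre-treatment score;
- B: A plus any candidate with a baseline test p < 0.05 (the plan's rule);
- C: A plus all 13 candidates, fixed in advance.

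From the documents: 48 per arm, and 36 per arm if 72 completers split equally. Assumed, because the documents are silent: correlation 0.5 between pre-treatment score and outcome, true effect 0.5 SD, total extra R² of the candidates from 0 to 0.4, complete data, two-sided 5% tests. Each cell has 6,000 runs, with Monte Carlo standard error about 0.3 points on type I error and 0.5 on power. All entries are percentages; ρ is the correlation among candidates.

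| Per arm, ρ | R² | Type I A / B / C | Power A / B / C | Type I, better of A and B |
|---|---|---|---|---|
| 48, 0 | 0 | 5.0 / 4.9 / 4.7 | 79.4 / 77.7 / 72.3 | 5.7 |
| 48, 0 | 0.1 | 5.2 / 4.7 / 5.3 | 78.6 / 77.8 / 78.8 | 5.7 |
| 48, 0 | 0.25 | 5.3 / 4.3 / 5.1 | 79.0 / 79.1 / 88.2 | 6.0 |
| 48, 0 | 0.4 | 5.2 / 3.8 / 5.2 | 80.3 / 81.3 / 96.6 | 6.0 |
| 36, 0 | 0 | 4.5 / 4.6 / 4.8 | 66.6 / 64.4 / 57.4 | 5.3 |
| 36, 0 | 0.1 | 5.5 / 4.9 / 4.6 | 67.6 / 65.7 / 64.9 | 6.3 |
| 36, 0 | 0.25 | 4.8 / 4.0 / 5.0 | 65.8 / 64.8 / 74.0 | 5.5 |
| 36, 0 | 0.4 | 4.6 / 3.5 / 5.4 | 67.1 / 66.4 / 88.4 | 5.5 |
| 48, 0.5 | 0 | 5.2 / 5.2 / 5.4 | 79.7 / 78.6 / 73.8 | 5.7 |
| 48, 0.5 | 0.1 | 4.7 / 4.5 / 4.7 | 79.4 / 79.6 / 79.3 | 6.1 |
| 48, 0.5 | 0.25 | 4.8 / 3.7 / 5.0 | 80.0 / 83.0 / 88.2 | 6.4 |
| 48, 0.5 | 0.4 | 4.8 / 4.1 / 4.9 | 79.2 / 85.5 / 96.8 | 7.6 |

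**Step 4: read the table.**

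- Rule against no rule (B − A): from −2.2 points (64.4 − 66.6) to +6.3 (85.5 − 79.2). The losses occur mainly when the candidates carry little or no prognostic information. A wider run with 23 non-prognostic candidates gave 80.0% without the rule and 77.2% with it, a loss of 2.8.
- Fixed list against rule (C − B) at R² 0.25 to 0.4: 5.2 to 15.3 points at 48 per arm and 9.2 to 22.0 at 36 per arm. At R² = 0, fixing all 13 loses 4.8 to 7.0 points, so a fixed list should be short. One covariate with R² = 0.25, fixed in advance, gives 92.2% against 81.0% under the rule.
- Choosing the better of A and B: type I error 5.3% to 7.6%.

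**Step 5: keep the named covariates in.** Models A to C omit the named list. Repeating the check with the five named baseline covariates always in the model gives a 43–46% chance of at least one spurious difference, type I error of 4.6–5.2%, and a power loss from the rule of about 0.5–2 points.

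**The case against.** The strongest defence is that the rule does little harm and some good. Selection uses baseline data and arm, never outcomes, so applied mechanically it cannot favour a positive result. It also protects the unlucky trial. With one candidate of R² = 0.25 at 48 per arm, among trials where that candidate is imbalanced, the model without it rejects a true null 22.7% of the time and the model with it 6.5%. The testing is described as preliminary and accepts unadjusted multiplicity over seven instruments, beside which a shift of 0 to 1.5 points is small.

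Most of this stands, and it limits the severity. It does not rescue the rule: fixing the same covariate in advance gives the same 6.5% in those trials and more power over all trials. The preliminary status is invoked only for multiplicity, not for leaving the model open.

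A reader might infer three stronger points that the documents do not support.

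- *The primary covariates as a whole are picked by chance.* They are not: the pre-treatment score and the six named covariates enter regardless.
- *The rule inflates false positives.* As written it is nominal to mildly conservative. Inflation needs an analyst who exploits the missing threshold.
- *The interval that clinicians are to judge comes from a data-selected model.* The efficacy section says the difference in mean change "for transdiagnostic CBT versus BAT control condition will be estimated via 95% CI", before and apart from the modelling text, and does not say that the interval comes from the adjusted model.

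**Conclusion.** The point holds as a minor to moderate flaw in a stated rule. Some additional covariates of the efficacy model are chosen by chance imbalance, and the model is not fixed until arm-level data are seen. With about 13 candidates, roughly a third to a half of trials would acquire at least one such covariate.

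The rule itself has a small effect: type I error about 3.5–5%, and at most about 3 points of power lost against the same model without it, with some gain where correlated candidates are strongly prognostic. The larger figure, about 5–15 points at 48 per arm, is the benefit forgone by not fixing covariates with moderate to strong prognostic value. It should not be read as damage done by the quoted sentence, and it vanishes if the candidates predict little. The risk of a type I error of 5.3–7.6% depends on discretion that the plan leaves open but does not invite.

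All sizes rest on the assumed 0.05 threshold, correlations, R² range, 0.5 SD effect and complete data.

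**What to change.** - Delete the between-arm baseline tests and the sentence that adds differing variables. Report baseline by arm with means, SDs and counts only.
- Replace the open list with a short closed list of baseline covariates, fixed before any arm-level data are examined: the pre-treatment score, principal diagnosis as the stratification factor, and a few variables expected to be prognostic, such as age and number of psychiatric comorbidities. The number of treatment sessions arises after randomisation and so falls outside such a list.
- Confine any adjustment prompted by observed imbalance to a labelled sensitivity analysis that does not replace the primary model.

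The cost is a few sentences of analysis-plan wording, with no extra data or staff. The one drawback is that an unlisted covariate that happens to be imbalanced is not adjusted for in the primary model; the sensitivity analysis covers that case.
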